7.3 Prohibited concomitant drugs and permitted concomitant drugs

7.3.1 Prohibited concomitant drugs

[Prohibited concomitant drugs]

The concomitant use of the following drugs* will be prohibited during the clinical study [Visit 1 (Day -29 to Day -1 before the start of study drug administration) to Visit 4 (Week 8)].

(*: including concomitant drugs that were administered at the start of observation period and prohibited in the package insert of the HMG-CoA reductase inhibitor)

1. EPA preparations or EPA/DHA preparations (including supplements)
2. Antidyslipidemic agents (except for HMG-CoA reductase inhibitors administered at the start of observation period)
 - Anion exchange resin, fibrates, nicotinic acid derivatives, probucol, phytosterols and others (elastase ES, dextran sulfate sodium, polyenephosphatidylcholine, pantethine, ezetimibe)
3. Pancreatic hormones
 - Insulin preparation
4. Androgens
 - Testosterone, methyltestosterone
5. Follicle hormone and luteinizing hormone
 - Estrogen and progestogen
6. Systemic steroids
7. Thyroid hormone

<Rationale>

1 to 7 Efficacy of the study drug may not be assessed accurately with these concomitant drugs.

7.3.2 Permitted concomitant drugs

Concomitant use of “HMG-CoA reductase inhibitors,” “antidiabetic drugs (except for insulin)” or “antihypertensive drugs” is allowed during the study period. However, for “HMG-CoA reductase inhibitors” and “antidiabetic drugs (except for insulin),” dose modification, addition of new treatment drugs, or change of treatment drugs shall not be allowed unless the principal investigator or investigator considers it necessary due to adverse events, etc.

7.4 Study subject management

The principal investigator or investigator shall instruct study subjects regarding the following:

- (1) Guidance for study subjects for improving lifestyle should not be changed or modified during the clinical study. Study subjects shall be instructed to avoid excessive exercise to the extent possible during the study period.
- (2) Study subjects shall be instructed not to consume alcohol after 9:00 pm 2 days before the hospital visit and not to consume food after 9:00 pm the day before the hospital visit until the test to be performed in the fasting state. Although water can be taken as desired on the day of blood collection, study subjects shall be instructed to visit the hospital in a fasting state in order that fasting morning samples can be collected.
- (3) Study subjects shall be instructed to avoid eating/drinking to excess, extreme change in dietary content (eating a high-fat meal, etc.) or excessive exercise, and spend time on a routine basis the day before the hospital visit.
- (4) Study subjects shall be instructed to visit the hospital according to the schedule and take the test as prescribed during the study period.
- (5) Study subjects shall be instructed to comply with the instructions or restrictions (taking the study drug, prohibited drugs for concomitant use, those allowed for concomitant use, etc.) during the study period.
- (6) Upon concomitant use of anticoagulants (warfarin potassium, etc.) or antiplatelet drugs (aspirin, etc.) listed under Precautions for Coadministration in the package insert of the study drug, study subjects shall be instructed to promptly report in the event of an adverse drug reaction, such as bleeding.
- (7) Study subjects must notify the principal investigator or investigator in advance if they receive treatment from other physicians. If treated by other physicians, the study subjects shall be instructed to promptly report the details of the treatment.

7.5 Criteria for discontinuation or withdrawal of a study subject

The principal investigator or investigator shall record the main reason for discontinuation of protocol treatment on the case report form (CRF) according to the classification described below. Refer to Section 9.1.11 for study subjects who withdraw from the study before randomization.

1. Adverse events

When the study subject had an adverse event that requires withdrawal of the study subject from the study because continued participation in the study would impose an unacceptable risk to the study subject's health, or when the study subject is unwilling to continue study participation because of the adverse event.

2. Major protocol deviation

When it is discovered after randomization that a study subject does not meet the eligibility criteria or is not adhering to the protocol, and continued participation in the study would impose an unacceptable risk to the study subject's health.

3. Lost to follow-up

When the study subject failed to make visits and could not be contacted despite the attempts to contact the study subject.

4. Voluntary termination

When the study subject wishes to withdraw from the study. The reason for discontinuation shall be obtained to the extent possible.

5. Study termination

When the sponsor or a committee such as the Ethical Review Board or regulatory authority has decided to terminate the study. Refer to Section 6.3.1 for details.

6. Pregnancy

When a female study subject was found to be pregnant.

Note: The study subject must discontinue the study immediately after she was found to be pregnant. Refer to Section 9.1.13 for the procedures.

7. Lack of efficacy

When efficacy of the study drug is not evident and continuation of the study may pose an unacceptable risk to the study subjects in the opinion of the principal investigator or investigator.

8. Others

When the principal investigator or investigator determined to terminate the study for other reasons.

The specific reasons should be recorded on the CRF.

7.6 Procedures for discontinuation of individual study subjects

The principal investigator or investigator shall terminate a study subject's study participation when the study subject meets the criteria described in Section 7.5. Individual study subjects may discontinue their study participation without giving a reason at any time during the study. Should a study subject's participation be discontinued, the primary reason for termination shall be recorded on

the CRF by the principal investigator or investigator. In addition, efforts shall be made to perform all tests/observations/evaluations scheduled at the time of discontinuation.

8.0 STUDY TREATMENT

8.1 Study drug

Generic name: Omega-3-acid ethyl esters

Chemical name: Ethyl icosapentate;

ethyl(5Z,8Z,11Z,14Z,17Z)-icosa-5,8,11,14,17-pentaenoate

Docosahexaenoic acid ethyl ester;

ethyl(4Z,7Z,10Z,13Z,16Z,19Z)-docosa-4,7,10,13,16,19-hexaenoate

8.1.1 Dose and administration method

For subjects who were allocated to the omega-3 group, omega-3-acid ethyl esters 2 g is to be orally administered immediately after meal twice daily for 8 weeks. The principal investigator or investigator chose patients needed treatment with omega-3-acid ethyl esters 4 g/day as a result of assessment. In principle, the dosage prescribed to the study subject should not be changed until the end of the study. Since the study subject should visit the study site in the fasting state, the post-breakfast dose, if any, should be administered immediately after the first meal in the day after completion of the prescribed test.

Medication should be started the day after completion of all the tests at Week 0.

8.1.2 Concomitant drugs

The “HMG-CoA reductase inhibitors” or “antidiabetic drugs (except for insulin)” taken at the start of observation period should continue without dose modification during the study period. Addition or change of these drugs are not allowed.

8.1.3 Overdose of the study drug

Overdose is defined as intentional or accidental administration of the study drug at a higher dose than that specified in the protocol, either by a health professional or by the study subject.

To consistently collect important safety information about overdose, the principal investigator or investigator(s) shall record all cases of overdose on the “Overdose” page of the CRF, irrespective of the presence or absence of accompanying adverse event. Adverse events associated with overdose shall be recorded on the “Adverse events” page of the CRF, in accordance with the procedures described in Section 10.0, “Adverse Events.”

In addition, serious adverse events associated with overdose shall be recorded in accordance with the procedures described in Section 10.2.2, "Collection and reporting of serious adverse events."

In the event of overdose, the principal investigator or investigator shall treat the subject as required based on symptoms.

8.2 Allocation of the study drug and administration procedure

The principal investigator or investigator shall access the Case Registration Web System to allocate the study subjects. The principal investigator or the designee shall notify the information required for allocation in addition to the study subject identification (ID) code. Then, subjects will allocate to omega-3 group or control group through the Case Registration Web System. The principal investigator or investigator shall prescribe the study drug and/or HMG-CoA reductase inhibitor according to the notification, and record the prescribed dose for each study subject in the CRF.

8.3 Preparation and storage of allocation list

The allocation responsible person (designated by the sponsor) shall create an allocation procedure. Information on the allocation shall be kept in a safe place and shall not be available to anyone other than authorized persons, to secure independency from the clinical study.

Using fasting TG values and ages as stratified factors, stratified allocation shall be performed at the Registration Center at the start of treatment period. For allocation, the Registration Center shall use the Allocation Procedure for Stratified Allocation prepared by the allocation responsible person.

9.0 CLINICAL STUDY PROTOCOL

9.1 Clinical study procedures

The principal investigator or investigator shall collect data in accordance with the procedure below. In principle, all the tests, observations, and evaluations of study subjects shall be performed by the same principal investigator or investigator with the exception of the specific 20-lipoprotein fraction. The study schedule is provided in Appendix A.

9.1.1 Informed consent

The procedures for obtaining informed consent are described in Section 15.3.

Consent shall be obtained from the study subject before initiation of study procedures.

Study subject ID code is given to each study subject from whom informed consent was acquired and who was randomized. The study subject ID code shall be used throughout the study period and shall not be changed.

9.1.2 Demographic data, medical history, and previous treatment drugs

Demographic data shall be collected regarding date of birth, gender, time (year/month) of onset (or diagnosis) of hyperlipidemia, frequency of consumption of fish (almost every day, once/2 days, 1 to 2 times/week, almost never), HMG-CoA reductase inhibitor administered before start of observation period, and smoking and drinking history.

Medical history data shall be collected regarding clinically problematic diseases or symptoms that disappeared or were terminated within 1 year from initiation of screening period and that related to target conditions. When the symptoms or disease continues, it shall be considered as a concurrent disease (Refer to Section 9.1.7).

Previous treatment drug data shall be collected regarding all drugs used within 12 weeks before the initiation of screening period and that are related to criteria for eligibility and assessment of efficacy.

9.1.3 Physical examination

All subsequent physical examinations after the start of study drug administration shall be assessed for clinically significant changes from the baseline examination.

9.1.4 Body weight, height, and BMI

Body weight and height shall be measured. The sponsor shall calculate the BMI using the following formula.

Body Mass Index: $BMI = \text{body weight (kg)} / [\text{height(m)}]^2$

Height shall be measured to the nearest whole number in centimeters. Body weight shall be measured to one decimal place in kilograms. The result of BMI shall be shown to one decimal place.

Example:

Height = 176 cm, body weight = 79.2 kg, BMI = $79.2/1.76^2 = 25.6 \text{ kg/m}^2$

9.1.5 Vital signs

For vital signs, blood pressure in sitting position (after resting for at least 5 minutes) and a pulse rate (bpm) shall be measured.

When timing for the vital signs measurement overlaps with blood collection, priority shall be given to blood collection, and the vital signs shall be measured within 30 minutes before or after the blood collection.

9.1.6 Concomitant drugs

Concomitant drugs are all drugs to be given in addition to the study drug. Drugs prescribed by doctors or the over-the-counter medicines purchased by the study subjects shall be included. At every hospital visit of the study subject, the name, dose and dose regimen, route of administration and treatment duration should be investigated for the drugs (including vitamin compound, over-the-counter medication, and Chinese medicine) used other than the study drug from the start of the screening period to the completion of the clinical study. HMG-CoA reductase inhibitor administered before start of observation period is not treated as concomitant drug.

9.1.7 Concurrent disease

A concurrent disease shall be defined as a disease or symptom present at the start of the screening period or observed from the start of the screening period until before the start of study drug administration. Clinically problematic laboratory test data, ECG findings, and abnormal physical examination findings observed at the start of the screening period shall be considered as a concurrent disease at the discretion of the principal investigator or investigator. The content of concurrent disease (diagnosis) shall be investigated.

9.1.8 Food and drink consumption before the visit

The principal investigator or investigator shall confirm with the study subject about food and drink consumed before the visit at every visit.

- Alcohol should not be consumed from 9:00 pm 2 days before the visit, and food should not be consumed from 9:00 pm the day before the visit until the fasting test.
- Excessive eating/drinking and extreme change in dietary content should be avoided on the day before the fasting test.

9.1.9 Laboratory tests and the specific 20-lipoprotein fraction assay

According to the observation schedule (Appendix A), samples are to be collected in each study site for the following laboratory tests and the specific 20-lipoprotein fraction assay. The fasting test is to be performed under ≥ 10 -h fasting.

The principal investigator or investigator shall evaluate and keep the reported laboratory test results. Results of the specific 20-lipoprotein fraction assay shall be assessed by the chair and member of the Clinical Study Steering Committee.

Table 9.a Laboratory tests

Hematology^(a)	Serum chemistry^(a)
Platelet count	Total cholesterol, TG, HDL-C, LDH, AST, ALT, ALP, γ -GTP, CK(CPK)
Specific 20-lipoprotein fraction^(b), lipid content of each lipoprotein fraction^(b), mean particle size of LDL^(b), mean particle size of HDL^(b)	
Apoprotein, remnant lipoprotein	
Apolipoprotein A1 ^(a) , A2 ^(a) , B ^(a) , B-48 ^(a) , B-100 ^(c) , C-II ^(a) , C-III ^(a) , C-II/III ^(a) , E ^(a) , RemL-C ^(a)	
Others	Fatty acid fraction in total lipids^(a)
Lipoprotein lipase ^(c) , high-sensitive CRP ^(a)	24-fatty acid fraction, T/T, EPA/AA

(a) To be measured in PPD [redacted]

(b) To be assayed for the sub-class⁽⁶⁾ specified for each fraction number using HPLC in CCI [redacted] PPD [redacted]

Fraction No.	1	2	3	4	5	6	7	8	9	10	11	12	13	14	15	16	17	18	19	20
Particle diameter	>90	75	64	53.6	44.5	36.8	31.3	28.6	25.5	23	20.7	18.6	16.7	15	13.5	12.1	10.9	9.8	8.8	7.6
Sub-Class	Chylomicrons		large VLDL			medium VLDL	small VLDL	large LDL	medium LDL	small LDL	very small LDL			very large HDL	large HDL	medium HDL	small HDL	very small HDL		

(c) To be measured in PPD [redacted]

The principal investigator shall keep laboratory test reference values including the historical data with the exception of the specific 20-fraction assay using CCI [redacted]

9.1.10 Contraception

Female subjects of childbearing potential (e.g., nonsterilized or premenopausal female subjects) must use adequate contraception from signing on the informed consent throughout the study period. At the time of acquisition of informed consent from an applicable study subject, signature on the informed consent should be acquired only after explanation is made about what is the adequate

contraception and that the subject must avoid to be pregnant during the study period by use of the informed consent form until the subject thoroughly understands them.

9.1.11 Pregnancy

When a study subject was found to be pregnant during the study period, the fact that the female study subject participated in the study when she became pregnant with the details of the study drug should be transferred to her obstetrician upon agreement with her.

Pregnancy during the study period and until the day of the last study drug administration should be reported to the sponsor with the format separately specified.

9.1.12 Record of study subjects who are withdrawn before randomization

A CRF shall be created for all study subjects who have signed the consent form and withdrawn before randomization.

The following items are to be described on the CRF.

- Date of consent obtainment
- Date of birth
- Gender
- Eligibility
- Adverse events (with details, if any)
- Reason for discontinuation

The primary reason for withdrawal before randomization shall be recorded on the CRF according to the following classification:

- Adverse events
- Not satisfying at least one of the inclusion criteria or meeting any of the exclusion criteria
- Major protocol deviation
- Lost to follow-up
- Voluntary discontinuation (specify the reason)
- Study termination
- Pregnancy
- Others (specify the reason)

Study subject ID codes assigned to study subjects withdrawn from the study before randomization shall not be reused.

9.1.13 Record of randomization

Study subjects to be randomized shall meet all of the inclusion criteria and shall not meet any of the exclusion criteria according to 8.2 Section 8.2. The principal investigator or investigator shall specify the primary reason why the study subject cannot be randomized.

9.2 Compliance with study treatment of study subjects

The principal investigator or investigator shall confirm compliance with the study treatment with study subject at every visit. Throughout the study period, overall treatment compliance shall be checked in the interview and categorized into the 2 categories of “ $\geq 50\%$ or $< 50\%$ of the prescribed dose.” If poor compliance with study treatment (e.g., $< 50\%$ of the prescribed dose) has been found through the interview and does not improve, the study subject may be withdrawn from the study if appropriate for the circumstances.

9.3 Implementation time point of the tests and observation

The schedule for all tests, observations, and evaluations is shown in Appendix A. The principal investigator or investigator shall perform the tests, observations, and evaluations at the time points shown below.

9.3.1 Screening period (Visit 1)

At Visit 1 (Day -29 to Day -1 before the start of study drug administration), the study shall be explained using the informed consent form to the study subjects who meet the inclusion criteria (except for 3) in Section 7.1 and do not meet any of the exclusion criteria in Section 7.2, and consent shall be obtained in accordance with Section 15.3.

Tests, observations, and evaluations to be performed at Visit 1 (Day -29 to Day -1 before the start of study drug administration) are shown below.

- Informed consent
- Demographic data, medical history, previous treatment drug(s)
- Physical examination
- Height, body weight and BMI
- Vital signs
- Concomitant drugs
- Concurrent disease
- Laboratory tests (fasting)

Items to be checked: Food and drink consumption before visit

- Confirm that alcohol was not consumed from 9:00 pm 2 days before the visit and food was not consumed from 9:00 pm the day before the visit

- Confirm that excessive eating/drinking and extreme change in dietary content were not made on the day before the visit.

9.3.2 Treatment period (Visit 2)

In consideration of the results of tests and observation at Visit 1 (Day -29 to Day -1 before the start of study drug administration), the principal investigator and the investigator shall perform the following tests, observations, and evaluations for each study subject.

Items to be checked: Food and drink consumption before visit

- Confirm that alcohol was not consumed from 9:00 pm 2 days before the visit and food was not consumed from 9:00 pm the day before the visit
 - Confirm that excessive eating/drinking and extreme change in dietary content were not made on the day before the visit.
-
- Physical examination
 - Vital signs
 - Concomitant drugs
 - Concurrent disease
 - Laboratory tests

The principal investigator or the investigator shall give notification to the Registration Center (accessing to the Case Registration Web System) regarding study subjects in whom all the tests, observation and evaluation at Visit 2 (Day -15 to Day -1 before the start of study drug administration) have been completed and study drug administration was considered possible.

The principal investigator or the investigator shall prescribe the study drug at a dose notified from the Registration Center and tell the study subject to take the drug starting from the next day.

Refer to Section 9.1.11 for preparation of records relating to the study subjects withdrawn before randomization.

9.3.3 Treatment period (Visit 3)

In consideration of the results of tests and observation at Visit 2 (Day -15 to Day -1 before the start of study drug administration), the principal investigator and the investigator shall perform the following tests, observations, and evaluations for each study subject. If the study drug administration is discontinued, study subjects should, to the extent possible, undergo tests, observations, and evaluations required for the last visit within 3 days from the last dose taken.

Items to be checked: Food and drink consumption before visit

- Confirm that alcohol was not consumed from 9:00 pm 2 days before the visit and food was not consumed from 9:00 pm the day before the visit
 - Confirm that excessive eating/drinking and extreme change in dietary content were not made on the day before the visit.
-
- Physical examination
 - Vital signs
 - Concomitant drugs
 - Laboratory tests
 - Treatment compliance
 - Evaluation of adverse events

9.3.4 Completion (Visit 4) or discontinuation

Visit 4 is the last visit, and the principal investigator or the investigator shall perform the following tests, observations, and evaluations for each study subject. If the study drug administration is discontinued, study subjects should, to the extent possible, undergo tests within 3 days from the last dose taken.

Items to be checked: Food and drink consumption before visit

- Confirm that alcohol was not consumed from 9:00 pm 2 days before the visit and food was not consumed from 9:00 pm the day before the visit
 - Confirm that excessive eating/drinking and extreme change in dietary content were not made on the day before the visit.
-
- Physical examination
 - Vital signs
 - Concomitant drugs
 - Laboratory tests
 - Treatment compliance
 - Evaluation of adverse events

At completion of the clinical study, the status of all study subjects administered the study drug shall be recorded on the CRF.

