10.1.9 Actions taken for the study drug

Actions taken for the study drug shall be classified or defined as shown below.

Drug withdrawn	The study drug is discontinued because of an adverse event (including withdrawal by the study subject at his/her own discretion). When the study is discontinued but study drug administration is still continued, the classification should be “Dose not changed.”
----------------	--

Dose not changed	
The dose was not changed after the onset of the adverse event.
 
The study drug was discontinued, reduced, or increased because of another adverse event.
 
The study drug was discontinued or reduced for a reason other than the adverse event, e.g., inadvertence of the study subject.

Unknown	It has not been possible to determine what action has been taken because the study subject is lost to follow-up.
Not Applicable	The administration of the study drug had already been completed or discontinued before the onset of the adverse event.
Dose reduced	The dose of the study drug is reduced because of an adverse event (including dose reduction by the study subject at his/her own discretion).

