Appendix A Schedule for Study Procedures

Visit timing	Week	Screening period	Treatment period			Discontinuation ^(e)
	Day	-4	0	4	8	
Window (day)		-29 to -1	-15 to -1	14 to 41	42 to 70	Within 3 days after the last dose
Visit No.		1	2	3	4	
Informed consent		X				
Inclusion/exclusion criteria		X				
Demographic data, medical history, previous treatment drug(s)		X				
Physical examination		X	X	X	X	X
Height		X				
Body weight		X				
BMI		X				
Vital signs		X	X	X	X	X
Concomitant drugs ^(a)		X	X	X	X	X
Concurrent disease		X	X			
Laboratory tests						
Hematology/ Serum chemistry		X ^(c)	X	X	X	X
Specific lipoprotein fraction assay ^(b)		X ^(c)	X	X	X	X
Lipoprotein assay ^(b)		X ^(c)	X	X	X	X
Mean particle diameter of LDL/HDL ^(b)		X ^(c)	X	X	X	X
Fatty acid fraction in total lipids		X ^(c)	X	X	X	X
Others		X ^(c)	X	X	X	X
Study drug prescription			X	X		
Treatment compliance				X	X	X
Food and drink consumption before the visit			X	X	X	X
Evaluation of adverse events			←X→	←X→	←X	←X

(a) All concomitant drugs will be recorded.

(b) By HPLC

(c) To be performed before the Visit 2 tests

(d) Medication will be started the day after the completion of all the tests of Week 0. The start date of medication will be referred to as Day 1.

(e) To be performed to the extent possible

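### Cheap improvement: stopping study drug is not separated from leaving the study, so an omega-3 patient whose last dose is by Day 38 normally has no Week 8 value for the ANCOVA

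*Protocol*

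**What the plan says.** Protocol 9.3.4, which covers Visit 4 and discontinuation together, states: "If the study drug administration is discontinued, study subjects should, to the extent possible, undergo tests within 3 days from the last dose taken". Section 9.3.3 asks a patient who stops to "undergo tests, observations, and evaluations required for the last visit within 3 days from the last dose taken", again as far as possible. Appendix A has a separate discontinuation column timed "Within 3 days after the last dose". None of the three schedules a lipid sample after that.

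Under section 7.5 the investigator "shall record the main reason for discontinuation of protocol treatment on the case report form", using a list of eight reasons. Section 7.6 makes the same list the trigger for leaving: the investigator "shall terminate a study subject's study participation when the study subject meets the criteria described in Section 7.5". It adds that "efforts shall be made to perform all tests/observations/evaluations scheduled at the time of discontinuation".

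SAP section 2 sets Week 4 as Day 14-41 and Week 8 as Day 42-70 (reference Day 56), and takes the value closest to the reference date. SAP section 3 puts every randomised patient with at least one dose in the FAS. SAP 7.1(5) applies the ANCOVA to percent change from Week 0 to Week 8, SAP 10.2 rules out imputation, and SAP 6.1.3.1 tabulates one status, at the end of study.

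**The concern.** The discontinuation tests take the place of Visit 4. A patient who stops early and is willing to come back is given no clear Week 8 sample. Controls have no study drug to stop, so this route to a missing value exists only in the omega-3 arm, although controls can be lost for other reasons.

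If stopping is related to response or tolerance, the Week 8 ANCOVA leans towards omega-3 patients who stayed on drug. It is the only modelled comparison in the plan. No later change of analysis can recover a sample that was never drawn, so the remedy has to be in the protocol.

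**Working it through.** **Dates.** Inputs: Day 1 is the first dose (Appendix A). The latest discontinuation test is on last-dose day + 3 (9.3.3, 9.3.4, Appendix A). Week 4 is Day 14-41 and Week 8 is Day 42-70 (SAP section 2).

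| Last dose | Latest test | Where the sample can fall |
|---|---|---|
| Day 10 or earlier | Day 13 | no window |
| Day 11-38 | Day 14-41 | Week 4 at most |
| Day 39-41 | Day 42-44 | Week 8 only if tested on Day 42 or later |
| Day 42 or later | Day 45 or later | Week 8 |

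Day 38 + 3 = Day 41, the last day of the Week 4 window. Day 38 is thus the latest last dose that cannot give a planned Week 8 value. Counting the last-dose day itself as the first of the three days would move this to Day 39. An unscheduled sample on Day 42-70 would be accepted by the SAP window, but none is planned. A patient who stops after Visit 3 still has a Week 4 value.

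**Later stops.** Take a last dose on Day 45, a discontinuation test on Day 48 and Visit 4 on Day 56. Both samples are in the Week 8 window, 8 and 0 days from the reference date. The closest-date rule would take the off-drug Day 56 value. Keeping Visit 4 therefore needs an explicit SAP rule for these patients.

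**Size.** The plan gives no stop rate and no expected effect, and Protocol 13.3 sets the sample size on feasibility, so it has no figure to reproduce. Assumptions:
- 25 evaluable patients per arm are reached as planned, and *k* further omega-3 patients have no Week 8 value;
- controls lose nobody;
- a patient who stopped keeps a share *r* of the retained patients' effect *d* (in SD units);
- the benchmark is the all-randomised effect, which is my choice and not a target that the documents state.

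With f = k/(25+k), the overstatement is 1/(1 − f + f·r) − 1.
- r = 0: 26/25, 28/25 and 30/25, minus 1, give 4%, 12% and 20% for k = 1, 3, 5.
- r = 0.5: 26/25.5, 28/26.5 and 30/27.5, minus 1, give 2.0%, 5.7% and 9.1%.

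The shift in SD units is d·f·(1 − r). The 95% half-width for 25 against 25, as a simple two-mean comparison, is t(0.975, 48)·√(2/25) = 0.569 SD.
- d = 0.5, r = 0: 0.5 × 1/26 = 0.019, 0.5 × 3/28 = 0.054 and 0.5 × 5/30 = 0.083 SD, or about 3%, 9% and 15% of 0.569.
- d = 0.3, r = 0: 0.012, 0.032 and 0.050 SD, or 2%, 6% and 9%.
- d = 0.8, r = 0: 0.031, 0.086 and 0.133 SD, or 5%, 15% and 23%.

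**The case against.** **The protocol does not withdraw everyone who stops.** A reader might infer from 7.5 and 7.6 that every drug stop ends participation. The text does not go that far. Items 1, 2 and 7 of 7.5 need unacceptable risk or, for item 1, unwillingness to continue. Section 7.4(4) says "Study subjects shall be instructed to visit the hospital according to the schedule and take the test as prescribed during the study period", and section 10.1.9 provides for a case "When the study is discontinued but study drug administration is still continued", so drug status and study status can differ. This stands: a willing patient is not expressly withdrawn. But 7.4(4) is general, while 9.3.3, 9.3.4 and Appendix A are specific to drug stops and put the 3-day tests where Visit 4 would be. The general line does not settle what happens at Week 8.

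**The exceptions leave few patients to gain.** Partly true. The gain is in patients who stop for tolerability without undue risk, are withdrawn for poor compliance under 9.2, or stop under the lack-of-efficacy or other-reasons items, and can still attend one visit.

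**The objective is the effect of 8 weeks of treatment, so near-on-drug samples are what is wanted.** This is fair, and the choice of target is a genuine trade-off. But for a last dose by Day 38 the 3-day sample is not used at Week 8 either, so the plan serves neither target for these patients.

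**Drug stops are already visible.** Exposure duration, adverse events leading to discontinuation, a listing of discontinued patients and the CRF reason are all planned. This stands as to reporting, but none of it supplies a Week 8 value.

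**The study is exploratory.** Also true. The protocol's own analysis is descriptive at each time point, and the SAP gives mean differences at Week 4, where many early stoppers contribute. That limits what is at stake.

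**Conclusion.** The point holds as a cheap improvement. The protocol does not separate stopping study drug from leaving the study. An omega-3 patient whose last dose is by Day 38 is in the FAS but normally absent from the Week 8 ANCOVA, with nothing imputed.

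A reader might go further and call the Week 8 result materially biased. The documents do not support that. They give no stop rate and do not name the all-randomised effect as the target. Under the assumptions above the overstatement is 4%, 12% or 20% for 1, 3 or 5 lost patients at r = 0, and about half of that at r = 0.5. This is small against the sampling error. If the drug has no effect and stopping is unrelated to prognosis, there is no bias. The date cut-off is firm to within one day; the size is illustrative only.

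**What to change.** **Protocol (7.5, 7.6, 9.3.3, 9.3.4, Appendix A) and CRF.** Record *stopped study drug* and *left the study* as separate items. A patient in either arm who stops or changes treatment, and is willing and safe to attend, still gives the scheduled Visit 4 fasting sample (Day 42-70) in addition to the 3-day tests. Exceptions: withdrawn consent, loss to follow-up, study termination, pregnancy, or a visit that is itself an unacceptable risk. The compliance rule in 9.2 can stay.

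**SAP (2 and 7.1).** Run the Week 8 FAS ANCOVA with the Visit 4 value, and show beside it the on-treatment version that the plan now gives. Where a discontinuation sample and a Visit 4 sample both fall in Day 42-70 (last dose from about Day 39), state that the first analysis uses Visit 4 and the on-treatment version uses the discontinuation sample. Do not leave this to the closest-date rule. For a last dose by Day 38, Visit 4 is the only planned sample in the Week 8 window, so the first analysis needs no special rule.

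**Cost.** Some short wording changes, and a few already scheduled visits kept. The Visit 4 estimate may be somewhat smaller because it includes off-drug values.
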